7.3.3 Patient Reported Questionnaires

In order to ensure accurate and unbiased subject questionnaire completion the following guidelines should be adhered to:

- The mPQI-I should be completed by the subject (with the caregiver's assistance, if necessary) prior to the visit (expected to be performed at the beginning of the bladder diary collection period). If it has not been completed prior to the visit it should be completed as the first activity at the visit
- The I-QoL and EQ-5D-5L should be completed by the subject (with the caregiver's assistance, if necessary), at the beginning of the site visit
- Questionnaires should be checked for completeness, in the subject's presence (every question should be answered)
- Study site personnel should not change responses on the questionnaires.

7.3.3.1 *Incontinence Quality of Life*

The I-QoL is a highly used, widely recommended, validated, disease-specific questionnaire designed to measure the effect of UI on subjects' QoL [21, 22, 23, 24]. It contains 22 items covering three domains of QoL:

- Avoidance and limiting behaviour
- Psychosocial impact
- Social embarrassment.

Subjects use a 5-point response scale with values ranging from 1 (extremely) to 5 (not at all). Each domain can be scored separately, and a total score can be calculated. Higher scores represent a better QoL.

7.3.3.2 *EuroQol 5-dimension 5-level*

The EQ-5D-5L is a widely used non-disease-specific, validated instrument developed by the EuroQol Group (Rotterdam, The Netherlands, www.euroqol.org) to assess health status. It consists of five dimensions covering:

- Mobility
- Self-care
- Usual activities
- Pain/discomfort
- Anxiety/depression.

Each dimension has five responses and therefore records five levels of severity.

The EQ-5D-5L also contains a visual analogue scale to record the subject's self-rated health.

7.3.3.3 *Modified Patient Global Impression of Improvement*

The subject's global impression of treatment response will be assessed using the mPGI-I scale. The mPGI-I will be completed on the electronic device used for the bladder diary. It should be completed before the visit, but may be completed at the beginning of the visit if not completed beforehand.

Subjects will assess any change in their UI compared to the situation immediately prior to their most recent treatment using a 7-point rating scale ("Very much better", "Much better", "A little better", "No change", "A little worse", "Much worse", "Very much worse").

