3.2.2 Secondary Efficacy Endpoints and Evaluations

3.2.2.1 Overview of Secondary Measures

Mean change from study Baseline (assessed at Screening) or from treatment cycle baseline (assessed at Retreatment Assessment Visit) to post-treatment timepoints (timepoints listed in [Table 4](#) and [Table 5](#)):

- Bladder diary measures:
 - weekly number of UI episodes
 - daily urinary frequency (total, spontaneous void only, CIC only)
 - 24-hour voided volume (total, spontaneous void only, CIC only)
 - volume per void (total, spontaneous void only, CIC only).
- Urodynamic filling cystometry measures:
 - maximum cystometric capacity (MCC)
 - maximum detrusor pressure (MDP) during storage
 - volume at first involuntary detrusor contraction (Vol@1stIDC) (subjects without a post-treatment IDC will have their Vol@1stIDC imputed from their MCC)
 - maximum detrusor pressure at first involuntary detrusor contraction (PdetMax@1stIDC)
 - end fill pressure (EFP)
 - detrusor compliance (DC).
- Patient-reported outcome questionnaires:
 - incontinence quality of life (I-QoL) total summary score
 - EuroQol 5-dimension 5-level (EQ-5D-5L)
 - modified patient global impression - improvement (mPGI-I) score (to be assessed at each timepoint without comparison to baseline).

Proportion of subjects at post-treatment timepoints following the first and subsequent treatments with:

- no episodes of UI (i.e. continence is achieved)
- UI response at several levels (i.e. $\geq 30\%$ improvement, $\geq 50\%$ improvement, $\geq 75\%$ improvement etc.)
- no IDCs on urodynamic assessment (i.e. urodynamic cure is achieved).

Duration of effect following the first and subsequent treatments measured by:

- time to request retreatment

- time to eligibility for retreatment
- time between treatments.

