- 12) Ability to complete all study requirements in the opinion of the investigator, including regularly completing the 7-day bladder diary and attending all scheduled study visits. The caregiver may assist with the completion of study documentation and procedures (including the bladder diary and questionnaires), if required.

The following inclusion criteria will be assessed following completion of screening bladder diary:

- 13) An average of at least two episodes per day of UI recorded on the screening bladder diary.

CC [REDACTED]

[REDACTED]

[REDACTED]

[REDACTED]

[REDACTED]

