9.2 Sample Size Determination

The sample size is based on the ability to detect a statistically significant treatment difference in the weekly number of UI episodes at Week 6 following treatment in the two Dysport[®] arms compared to the placebo arm.

Assuming a decrease of 21 UI episodes per week in each Dysport[®] arm and a decrease of 12 UI episodes per week in the placebo arm, with a common standard deviation of 20 UI episodes, 80% power, and an alpha of 0.025 (as testing of both the 600 U and 800 U doses vs. the placebo dose will be performed simultaneously), a sample size of N=96 subjects per dose group for the primary analysis (a total of 288 subjects) is needed.

Assuming a treatment group random allocation ratio 1:1:1, a sample size of 106 subjects in each treatment group will have 80% power to detect a difference in UI of 9 episodes (the difference between UI in Dysport[®] 600 U and Dysport[®] 800 U groups and in placebo group assuming a common standard deviation equal to 20 episodes and a dropout rate equal to 10% with a 0.025

two-sided type one error rate. A total of 318 subjects would therefore need to be enrolled. However, in order to ensure that the development program will deliver adequate Dysport exposure data to meet ICH E1 guideline recommendations, a total of 330 subjects are planned to be randomised.

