7.6.3 Primary Efficacy Analysis

The primary efficacy endpoint is mean change in the weekly number of UI episodes from study baseline to Week 6 after the first treatment. Seven-day bladder diaries that contain data recorded on at least 5 days will be included in the analysis.

As all subjects should have visits up to and including week 12, but thereafter visits are dependent on whether the subject receives retreatment, statistical testing between treatment groups will be performed only up to Week 12, inclusive. Descriptive statistics table will present any timepoint.

Weekly number of UI episodes and the mean change from study baseline will be presented for the DBPC Cycle. The mixed model repeated measures (MMRM) analysis will be conducted with the change of the weekly number of UI episodes from study baseline as response variable. Fixed effect variables include treatment group, visit (Week 2, Week 6 and Week 12), treatment-by-visit interaction, stratification variables [the aetiology of NDO and prior intradetrusor BTX-A usage for UI] and study baseline value of weekly number of UI episodes. Random effect will include the subject effect. An unstructured covariance matrix will be specified in the mixed

model to account for within subject correlation. If model fails to converge, the structure of first order autoregressive AR (1), compound symmetry (CS) or variance components (VC) will be used.

The least square means (LSMEANS) of the change of weekly number of UI at each visit in each group with standard error, the difference of mean between the two treatment groups at each visit, the 95% CI of the difference and the p-value for treatment group will be presented. The comparison of main interest will be treatment difference at Week 6.

The SAS codes of MMRM for reference are below.

```
CCI  
[Redacted SAS code for MMRM]
```

The validity of the model assumptions of normality will be investigated using residual plots. The LS means of change from study baseline for weekly UI in the DBPC and Dysport Cycles will be presented in line plots by treatment groups.

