7.6.5 Hierarchical Analysis of Secondary Efficacy Endpoints

As specified in Section 7.6.12, a hierarchical analysis will be performed in the order listed for the following six secondary efficacy endpoints at Week 6 after the first IMP administration:

- 1) Mean change from study Baseline in the MCC
- 2) Mean change from study Baseline in the MDP during storage
- 3) Mean change from study Baseline in the Vol@1stIDC
- 4) Proportion of subjects with no episodes of UI (i.e. continence is achieved)
- 5) Proportion of subjects with no IDCs during storage
- 6) Mean change from study Baseline in the I-QoL total summary score

The Derivation rules are specified in Section 3.2 and Appendix II.

For 1), 2) and 3), an ANCOVA model will be fitted using the “mean change” endpoint, as the response variable to obtain the p-value of treatment groups. The model will be the same as the sensitivity analyses for the primary efficacy endpoint in 7.6.4.2. The LSMEANS of the mean change from study baseline at Week 6 in each group with standard error, the difference of mean between the two treatment groups, the 95% CI of the difference and the p-value for treatment group will be presented.

For 4), a logistic generalised linear mixed model (GLMM) for repeated measures will be fitted for UI responses using repeated measurements at Week 2, Week 6, and Week 12. The “proportion of subjects with no episodes of UI” will be analysed as a response variable, the model will include treatment group, stratification variables, study baseline value, visit (week 2, week 6 and week 12), study baseline*visit and treatment*visit interactions as fixed effect. The study baseline value will be weekly number of UI episodes. The logistic GLMM is fitted using the logit link and the binomial distribution. Odds ratios, 95% CIs of odds ratio, and p-values for treatment group comparisons at each visit (week 2, week 6 and week 12) will be presented.

The SAS codes of GLMM for reference are below.

```
CCI
[Redacted SAS code]
```

CCI
[Redacted]
[Redacted]
[Redacted]

For 5), a logistic regression model will be performed with “proportion of subjects” as the response variable. The model will include treatment group, and stratification variables.

Odds ratio, 95% CI of odds ratio, and p-value will be presented.

The SAS codes of logistic regression for reference are below.

CCI
[Redacted]
[Redacted]
[Redacted]
[Redacted]
[Redacted]
[Redacted]
[Redacted]
[Redacted]

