7.6.6 Other Analysis of Secondary Efficacy Endpoints

The analysis of efficacy of the above-mentioned endpoints (primary endpoint and secondary endpoints included in the hierarchical analysis) will be conducted at timepoints other than Week 6 in the DBPC Cycle and is described below (except urodynamic endpoints as only performed at Week 6). The analysis of other secondary endpoints (see Section 3.2) is also described below.

Descriptive summaries will be performed for the DBPC Cycle and by Dysport Cycles (i.e. Dysport Cycle 1, Dysport cycle 2 ...), see the schematic diagram in Section 7.1.

Statistical comparison analyses are only applicable for the DBPC treatment cycle. Analyses between treatment groups, Dysport 600 U vs. Placebo, and Dysport 800 U vs. Placebo will be performed accordingly using GLMM and MMRM as mentioned below for each endpoint. As all subjects should have visits up to and including week 12, but thereafter visits are dependent on whether the subject receives retreatment, statistical testing between treatment groups will be

performed only up to Week 12, inclusive. All secondary endpoints not included in the hierarchical analysis are considered as exploratory endpoints and will therefore be analysed for exploratory purposes only to compare each Dysport dose to placebo, alpha at 0.05 level.

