For the DBPC Cycle for I-QOL and EQ-5D-5L, mean change from study baseline to Week 6 and Week 12, will be analysed using MMRM, similar to the primary efficacy analysis. Mean mPGI-I score at Week 2, Week 6, Week 12 will be analysed as a response variable, using MMRM as in the supportive primary analysis, without baseline factor for mPGI-I.

The LS means of change from study baseline in DBPC cycle for I-QoL total summary score at all timepoints will be presented in a line plot by treatment groups up to Week 12.

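### Read directly, the SAP's mPGI-I model leaves out baseline weekly incontinence: a small, avoidable loss of precision on an exploratory endpoint

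*Protocol*

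**What the plan says.** - **The scale.** Protocol 7.3.3.3: "Subjects will assess any change in their UI compared to the situation immediately prior to their most recent treatment using a 7-point rating scale". There is no pre-treatment mPGI-I, and Protocol 3.2.2.1 accordingly lists the score as "to be assessed at each timepoint without comparison to baseline".
- **The mPGI-I model.** SAP 7.6.6.3 takes the mean score at Weeks 2, 6 and 12 as the response, "using MMRM as in the supportive primary analysis, without baseline factor for mPGI-I".
- **The model it borrows.** The MMRM in SAP 7.6.3 has treatment, visit, treatment-by-visit, the two stratification variables and one baseline term: "study baseline value of weekly number of UI episodes".
- **Availability of that term.** Inclusion criterion 13 (Protocol 4.1) requires "An average of at least two episodes per day of UI recorded on the screening bladder diary".
- **Use elsewhere.** For the proportion of subjects who are continent, SAP 7.6.5 says: "The study baseline value will be weekly number of UI episodes".
- **Status.** SAP 7.6.6: "All secondary endpoints not included in the hierarchical analysis are considered as exploratory endpoints". The mPGI-I is not among the six hierarchical endpoints.

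**The concern.** The lack of a baseline on the mPGI-I's own scale is unavoidable and is not at issue. The baseline term in the borrowed model was never an mPGI-I value; it is the weekly UI count. The mPGI-I asks how UI has changed from the state before treatment, so the pre-treatment UI level is an obvious candidate prognostic covariate, and the trial already collects it to decide eligibility.

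Without it, the Dysport-versus-placebo estimates are not adjusted for chance differences between arms in baseline UI, and they carry any variance that baseline UI would have explained. Adjustment for aetiology and previous BTX-A use is not said to be removed. At stake is how tightly the plan estimates the one outcome in which subjects globally rate their own improvement.

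**Working it through.** **Check of the design inputs.** The documents give no power or effect size for the mPGI-I. Their only sample-size figure is for the primary endpoint (Protocol 9.2): "80% power to detect a difference in UI of 9 episodes", with SD 20 and two-sided alpha 0.025.

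n per arm = 2 × (z for alpha/2 + z for power)² × (SD/difference)² = 2 × (2.241 + 0.842)² × (20/9)² ≈ 94. The exact t calculation gives 96 (power 0.804 at 96 and 0.799 at 95), so the plan's 96 per group is reproduced. Nothing below changes it.

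**Precision for the mPGI-I.** Inputs:
- 110 subjects per arm, the two placebo sequences of 55 being pooled (Protocol 3.3.1).
- 10% dropout by Week 6 (SAP 2.3), leaving 110 × 0.9 = 99 evaluable per arm.
- Two-sided alpha 0.05 for endpoints outside the hierarchy (SAP 7.6.6).
- Share of residual variance explained by baseline UI, R² = r²: not in the documents, so assumed.

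Adding the covariate multiplies residual variance by (1 − R²). The standard error is multiplied by √(1 − R²), and the equivalent gain in sample size is 1/(1 − R²).
- R² = 0.02: √0.98 = 0.990, a 1.0% lower SE; 1/0.98 = 1.02.
- R² = 0.10: √0.90 = 0.949, a 5.1% lower SE; 1/0.90 = 1.11.

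Over a wider range, take an effect that has 80% power unadjusted at 99 per arm. Adjusted power is Φ[(1.960 + 0.842)/√(1 − r²) − 1.960]:

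| assumed r | fall in SE | adjusted power | unadjusted n per arm to match |
|---|---|---|---|
| 0 | 0% | 80.0% | 99 |
| 0.1 | 0.5% | 80.4% | 100 |
| 0.2 | 2.0% | 81.6% | 103 |
| 0.3 | 4.6% | 83.6% | 109 |
| 0.4 | 8.3% | 86.4% | 118 |
| 0.5 | 13.4% | 89.9% | 132 |

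The 2% to 10% range for R² corresponds to r of about 0.14 to 0.32.

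**Chance imbalance.** A one-standard-error difference in baseline UI between two arms of 110 is √(2/110) = 0.135 SD. It moves the unadjusted estimate by r × 0.135 SD, which is 0.04 SD at r = 0.3.

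**Validity.** A simulated single-visit 7-point score (99 per arm, 6,000 runs per setting, r = 0, 0.3 and 0.5 on the underlying scale) gave type I error of 0.051 to 0.055 without the covariate and 0.052 to 0.053 with it, against a nominal 0.05. For a 0.4 SD shift, power went from 0.776 to 0.777 at r = 0, from 0.773 to 0.809 at r = 0.3, and from 0.779 to 0.873 at r = 0.5.

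**The case against.** The strongest reply is that the SAP follows a coherent convention: a baseline covariate is the outcome's own baseline. Continence uses the weekly UI count because it is derived from that diary, and the model for absence of involuntary contractions has only treatment and strata. On that view the mPGI-I simply has no baseline to use. This explains the choice, but it is no reason to leave out a prognostic covariate already in hand. The protocol's instruction against comparison with baseline means that no change score is formed; it does not bar covariates.

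Four other objections stand and limit the point:
- **Wording.** The phrase may record only that no baseline mPGI-I exists, and the reference code is redacted. The supportive primary analysis it cites is not clearly identified; SAP 7.6.4.1 uses that adjective for the per-protocol run. Either way, the sentence does not tell a programmer plainly whether baseline UI stays in.
- **Proxy.** The scale refers to the state just before treatment. The diary is completed in a screening period of up to 30 days, with treatment up to 14 days later, and both intervals can be extended.
- **Size.** No document shows that the baseline UI count predicts the mPGI-I.
- **Completeness.** A reader might infer that every randomised subject has a baseline count. The documents support this only for eligible subjects; someone randomised in deviation might lack a valid diary and would drop out of the adjusted model.

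**Conclusion.** The point holds as a minor improvement. On the direct reading of SAP 7.6.6.3, the mPGI-I model omits a relevant covariate that should exist for all eligible subjects. The loss is in precision only: about 1% to 5% of the standard error if baseline UI explains 2% to 10% of residual variance, and none if it explains nothing. That range is assumed.

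A reader might infer that the unadjusted comparison is biased or its p-values unreliable. The documents do not support that: treatment is randomised, the strata are not said to be removed, and the simulated error rate stays near nominal without the covariate. Nor does the omission weaken the trial's confirmatory conclusions. The primary endpoint and the six hierarchical endpoints have their own models, and the mPGI-I is tested for exploratory purposes only.

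**What to change.** Before database lock, replace the closing phrase of the mPGI-I sentence in SAP 7.6.6.3 with an explicit list of the MMRM fixed effects: treatment group, visit, treatment-by-visit, aetiology of NDO, previous intradetrusor BTX-A use, and the study-baseline weekly UI count. In the same sentence, cite the intended model by section number instead of calling it the supportive primary analysis.

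The cost is one phrase in the SAP and one covariate in the code, with no new data. The statistical downside is negligible: one degree of freedom with about 297 evaluable subjects (3 × 99), plus the loss from this model of any subject randomised in deviation without a valid screening diary.

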8 ASSESSMENT OF SAFETY

8.1 Adverse Events

AEs will be monitored from the time that the subject gives informed consent and throughout the study (see [Section 3.4](#) for a definition of the study duration) and will be elicited by direct, nonleading questioning, or as volunteered by a subject. Further details for AE reporting can be found in [Section 8.1.2](#).

8.1.1 *Definition of an Adverse Event*

An AE is the development of an undesirable medical condition or the deterioration of a pre-existing medical condition following or during exposure to a pharmaceutical product, whether or not considered causally related to the product. An undesirable medical condition can be symptoms (e.g. nausea, chest pain), signs (e.g. tachycardia, enlarged liver) or the abnormal results of an investigation (e.g. laboratory findings, electrocardiogram). In clinical studies an AE can include an undesirable medical condition occurring at any time, including run-in or washout periods, even if no IMP has been administered.

This definition includes events occurring from the time of the subject giving informed consent until the end of the study (as defined in [Section 3.4](#)).

8.1.2 *Categorisation of Adverse Events*

8.1.2.1 *Intensity Classification*

AEs will be classified as mild, moderate or severe according to the following criteria:

- **Mild:** symptoms do not alter the subject's normal functioning
- **Moderate:** symptoms produce some degree of impairment to function, but are not hazardous, uncomfortable or embarrassing to the subject
- **Severe:** symptoms definitely hazardous to wellbeing, significant impairment of function or incapacitation.

8.1.2.2 *Causality Classification*

The relationship of an AE to IMP administration will be classified according to the following:

- **Related:** reports including good reasons and sufficient information (e.g. plausible time sequence, dose response relationship, pharmacology, positive dechallenge and/or rechallenge) to assume a causal relationship with IMP administration in the sense that it is plausible, conceivable or likely
- **Not related:** reports including good reasons and sufficient information (e.g. implausible time sequence and/or attributable to concurrent disease or other drugs) to rule out a causal relationship with IMP administration.

8.1.2.3 *Assessment of Expectedness*

The reference document for assessing expectedness of AEs/events in this study will be the current Dysport® IB.

8.1.2.4 *Laboratory Test Abnormalities*

Abnormalities in laboratory test values should only be reported as AEs if any of the following apply:

- They result in a change in IMP schedule of administration (change in dose, delay in administration, IMP discontinuation)
- They require intervention or a diagnostic evaluation to assess the risk to the subject

- They are considered as clinically significant by the investigator.

8.1.2.5 *Abnormal Physical Examination Findings*

New clinically significant findings (in the judgement of the investigator) should be reported as AEs.

8.1.2.6 *Other Investigation Abnormal Findings*

Abnormal test findings from any other investigation of the subject should be recorded as AEs if they:

- Are judged by the investigator to be clinically significant
- Result in a change in IMP dose or administration schedule
- Result in discontinuation of the IMP
- Require intervention or diagnostic evaluation to assess the risk to the subject.

8.1.2.7 *Definition of Urinary Tract Infection Adverse Events*

Refer to [Section 6.4.1.4](#).

8.1.2.8 *Adverse Events related to Progression of Neurogenic Detrusor Overactivity*

Natural progression or deterioration of the NDO symptoms under study will be recorded as part of the efficacy evaluation and should not normally be reported as an AE.

Natural progression or deterioration of the NDO symptoms under study should only be reported as an AE if:

- The investigator considers the progression/deterioration to be unusually severe or suggestive of accelerated disease; or
- The investigator considers the progression/deterioration to be caused directly by the IMP.

If there is any uncertainty about an AE being due to natural disease progression or deterioration of the NDO symptoms under study, then it should be reported as an AE.

8.1.2.9 *Neurological Adverse Events in Subjects with Multiple Sclerosis*

CCI
[Redacted text block]

8.1.2.10 *Suspicion of Exacerbation (Relapse) of Multiple Sclerosis*

CCI
[Redacted text block]

C
CI

8.1.2.11 *Adverse Events of Special Interest*

The effects of Dysport® and all BTX products may spread from the area of injection to produce symptoms consistent with BTX effects. These symptoms have been reported hours to weeks after injection. Remote spread of toxin that affects swallowing and breathing can be life threatening, and there have been reports of death. The risk of symptoms is increased in subjects who have underlying conditions (e.g. disorders of the neuromuscular junction) that would predispose them to these symptoms.

Dysport® is contraindicated in individuals with known hypersensitivity to any BTX preparation or to any of the components in the formulation.

Adverse events of special interest (AESIs) for Dysport® are AEs that suggest a possible remote spread of effect of the toxin or hypersensitivity. A list of preferred terms of AESIs is provided in the Statistical Analysis Plan (SAP).

All AEs will be monitored by the sponsor to determine if they meet the criteria of AESIs. These AESIs will be further analysed to determine if there is a plausible possibility that they represent distant spread of toxin or hypersensitivity. In order to perform the analysis, variables including alternate aetiology (medical history, concomitant medication, or diagnosis which could account for the symptoms), location of Dysport® administration, and temporal relationship to Dysport® administration will be considered by the sponsor.

8.1.3 *Recording and Follow-up of Adverse Events*

At each visit, the subject should be asked a nonleading question such as: “How have you felt since starting the new treatment/the last assessment?”

All observed or volunteered AEs, regardless of treatment group or suspected causal relationship to IMP, will be recorded on the AE page(s) of the eCRF. Events involving drug reactions, accidents, illnesses with onset during the treatment phase of the study, or exacerbation of pre-existing illnesses should be recorded (see also [Section 8.1.2.7](#) and [Section 8.1.2.10](#)).

Any AEs already recorded and designated as “continuing” should be reviewed at each subsequent assessment.

For all AEs, the investigator must pursue and obtain information adequate both to determine the outcome of the AE and to assess whether it meets the criteria for classification as a SAE requiring immediate notification to the sponsor or its designated representative. For all AEs, sufficient information should be obtained by the investigator to determine the causality of the AE (i.e. IMP or other illness). The investigator is required to assess causality and record that assessment on the eCRF. Follow-up of the AE, after the date of IMP discontinuation, is required if the AE or its sequelae persist. Follow-up is required until the event or its sequelae resolve or stabilise at a level acceptable to the investigator and the sponsor’s clinical monitor or his/her designated representative.

8.1.4 *Reporting of Serious Adverse Events*

All SAEs (as defined below) regardless of treatment group or suspected relationship to IMP must be reported immediately (within 24 hours of the investigator’s knowledge of the event) to the pharmacovigilance contact specified at the beginning of this protocol. If the immediate

report is submitted by telephone, this must be followed by detailed written reports using the SAE report form.

An SAE is any AE that:

- 1) Results in death
- 2) Is life threatening, that is any event that places the subject at immediate risk of death from the event as it occurred. It does not include an event that, had it occurred in a more severe form, might have caused death
- 3) Results in in-patient hospitalisation or prolongation of existing hospitalisation, excluding admission for social or administrative reasons (see further)
- 4) Results in a persistent or significant disability/incapacity, where disability is a substantial disruption of a person's ability to conduct normal life functions
- 5) Results in congenital anomaly/birth defect in the offspring of a subject who received the IMP
- 6) Is an important medical event that may not result in death, be life threatening, or require hospitalisation when, based upon appropriate medical judgement, may jeopardise the subject and may require medical or surgical intervention to prevent one of the outcomes listed in this definition. Examples of such medical events include allergic bronchospasm requiring intensive treatment in an emergency room or at home, blood dyscrasias or convulsions that do not result in in-patient hospitalisation, or the development of drug dependency or drug abuse.

In addition to the above criteria, any additional AE that the sponsor or an investigator considers serious should be immediately reported to the sponsor and included in the corporate SAEs database system.

- Hospitalisation is defined as any in-patient admission (even if less than 24 hours). For chronic or long-term in-patients, in-patient admission also includes transfer within the hospital to an acute/intensive care in-patient unit
- **Prolongation of hospitalisation** is defined as any extension of an in-patient hospitalisation beyond the stay anticipated/required in relation to the original reason for the initial admission, as determined by **the investigator or treating physician**. For protocol-specified hospitalisation in clinical studies, prolongation is defined as any extension beyond the length of stay described in the protocol. Prolongation in the absence of a precipitating, treatment emergent, clinical AE (i.e. not associated with the development of a new AE or worsening of a pre-existing condition) may meet criteria for "seriousness" but is not an adverse experience and thus is not subject to immediate reporting to the sponsor
- Preplanned or elective treatments/surgical procedures should be noted in the subject's screening documentation. Hospitalisation for a preplanned or elective treatment/surgical procedure should not be reported as an SAE unless there are complications or sequelae which meet the criteria for seriousness described above.

Any SAE must be reported immediately (within 24 hours), independent of the circumstances or suspected cause, if it occurs or comes to the attention of the investigator at any time during the study period.

Any AE/SAE with a suspected causal relationship to IMP administration occurring at any other time after completion of the study must be promptly reported.

The following information is the minimum that must be provided to the sponsor pharmacovigilance contact within 24 hours for each SAE:

- Study number
- Site number
- Subject number
- AE
- Investigator's name and contact details.

The additional information included in the SAE form must be provided to the sponsor or representative as soon as it is available. The investigator should always provide an assessment of causality for each event reported to the sponsor. Upon receipt of the initial report, the sponsor will ask for the investigator's causality assessment if it was not provided with the initial report. The investigator should report a diagnosis or a syndrome rather than individual signs or symptoms. The investigator should also try to separate a primary AE considered as the foremost untoward medical occurrence from secondary AEs which occurred as complications.

